5.6. Permitted dose adjustments and interruptions of study treatment

Dosing interruptions are permitted in the case of logistical reasons not related to study therapy, e.g., an unrelated event such as a COVID-19-related travel restriction or any other restriction or safety concern with the subject traveling to the study site. The reason for interruption should be documented in the patient's study record.

Once the restriction(s) leading to study drug interruption have been lifted and the Sponsor and Investigator agree that it is safe for the subject to resume study participation, the subject may be resumed on study therapy on a case-by-case basis upon discussion with the Sponsor. Subjects who received only 1 dose of study drug before interruption may either resume study drug with the second dose or may restart with the first dose of study drug if a sufficient amount of time has elapsed such that the expected PD effect has returned to baseline.

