5.4.1 Important Protocol Deviations Leading to Exclusion from the PP

Only those important protocol deviations considered to have a major effect on efficacy will lead to complete exclusion of the subject from the PP. For the purposes

Statistical Analysis Plan

Sponsor Name: Anthos
Sponsor Protocol ID: ANT-004

Covance Study ID: 000000189471

of this study, the list of subjects that have been identified as important protocol deviations leading to exclusion from the PP set is listed below. It is considered that the occurrences of any of these criteria might have an important influence on the primary efficacy endpoint.

Missed IMP dose

Missed FXI collection at V8, D91

Missed FXI collection at V2, Randomization

Out of window visit greater than 30 days

Most of the important protocol deviations leading to exclusion from the PP set require clinical or medical monitoring interpretation. These criteria will be reviewed prior to database lock. Important protocol deviations leading to exclusion from the PP set occurring during the study will be reviewed and approved by Anthos prior to database lock. Should additional important protocol deviations leading to exclusion from the PP set, not anticipated at the time of preparing this SAP, be identified during the study they will be documented in a SAP amendment and included in all relevant protocol deviation reviews and approvals.

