6.1 Time points and Visit Windows

Day 1 is defined as the day subjects receive the first dose of study drug. Relative days after Day 1 are calculated as (assessment date – Day 1 date) + 1. Relative days prior to Day 1 are calculated as (assessment date – Day 1 date). The day prior to Day 1 is Day -1.

Baseline is defined as the most recent result obtained prior to first administration of study medication. This occurs at visit 2 (day 1 pre-dose). If the assessment is not performed at visit 2, the value from visit 1 (screening) will be used. If this value is not present, there will be no baseline value.

Trough FXI levels will only be used if they are considered "on treatment". A measurement is considered "on treatment" if it is collected within 30 (± 5) days after the last administration of MAA868.

CONFIDENTIAL

Page 13 of 28

Statistical Analysis Plan

Sponsor Name: Anthos
Sponsor Protocol ID: ANT-004

Covance Study ID: 000000189471

All data will be analyzed using nominal study visits as defined in the schedule of assessments and eCRF. Unscheduled visits will be listed but not tabulated. No visit windows will be applied for summary and analysis.

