6.2 Handling of Dropouts, Missing Data, and Outliers

6.2.1 Study Discontinuation

Subjects who prematurely discontinue the study will undergo a study treatment discontinuation (TD) visit. Assessments performed at the TD visit are defined in appendix 4 of the protocol.

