7.7.1 Primary Efficacy Analysis

The primary analysis variable is a binary variable indicating whether a subject will achieve a certain percentage FXI inhibition at trough on Day 91. The response rate per treatment group will be calculated by number of subjects who achieve targeted FXI inhibition rate divided by the total number of subjects with an "on treatment" measurement in the treatment group. The dose regimens and targeted FXI inhibition achievement for Cohorts 1 and 2 are as follows:

CONFIDENTIAL

Page 19 of 28

Statistical Analysis Plan

Sponsor Name: Anthos

Sponsor Protocol ID: ANT-004

Covance Study ID: 000000189471

Cohort 1 (MAA868 120 mg monthly or placebo): Targeted to achieve $\geq 50\%$ FXI inhibition in 90% of subjects at trough (Day 91).

Cohort 2 (MAA868 180 mg monthly or placebo): Targeted to achieve $\geq 90\%$ FXI inhibition in 90% of subjects at trough (Day 91).

Cohort 3 (MAA868 TBD mg monthly or placebo): Targeted to achieve \geq TBD% FXI inhibition in 90% of subjects at trough (Day 91).

The "on treatment" trough FXI levels will be used for the primary analysis, where "on treatment" FXI level is defined as a value which is collected within 30 (± 5) days after the last administration of MAA868. The estimate of the responder rate (%) at Day 91 will be presented for each dose regimens of MAA868 together with 2-sided 90% confidence intervals computed via the Clopper-Pearson exact binomial method.

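### An in-window trough FXI value recorded as unscheduled is lost from the responder rates, and one drawn at the TD visit has no stated route into them

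*SAP*

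**What the plan says.** **Time definition.** SAP 6.1 uses a trough FXI value only if it is on treatment, that is "collected within 30 (± 5) days after the last administration of MAA868". SAP 7.7.1 says of such on-treatment values that "trough FXI levels will be used for the primary analysis", and its denominator counts only subjects in the arm who have one. SAP 7.7.2 repeats the analysis at Days 31 and 61.

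**Visit rule.** The same SAP 6.1 says "All data will be analyzed using nominal study visits as defined in the schedule of assessments and eCRF", then "Unscheduled visits will be listed but not tabulated", then "No visit windows will be applied for summary and analysis". SAP Table 1 (section 7.1) tabulates FXI inhibition at the trough visits and carries TD as a separate visit label.

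**TD visit.** SAP 6.2.1: "Subjects who prematurely discontinue the study will undergo a study treatment discontinuation (TD) visit". Protocol Table 9 marks free FXI in the TD column. Neither document maps a TD value to Day 31, 61 or 91.

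**Missing values.** SAP 6.2.2 uses observed data without imputation, and SAP 7.7.3 plans no sensitivity analysis.

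**Other PK/PD data.** SAP 7.9 summarises concentrations and PD parameters by scheduled visit. SAP 4.1 uses actual times for PK parameters and individual plots, and planned times for mean plots.

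**The concern.** A trough is a matter of elapsed time, and the SAP says so. Yet the only way into the responder tables is the visit label. The two rules operate in series: the label decides whether a value is a candidate, and the 30 ± 5 day filter then decides whether it stays. Nothing works in the other direction, so a value that satisfies the time definition under another label is not brought in.

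Two kinds of sample are exposed. One is a redraw entered as an unscheduled visit, for example after a failed Day 91 sample. The other is the FXI sample of a TD visit that happens to fall in the window after the subject's last dose. Off-schedule visits are foreseeable: Protocol 5.6 says "Dosing interruptions are permitted in the case of logistical reasons not related to study therapy", and SAP 7.4 plans listings of COVID-19-related dosing deviations and missed visits.

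At stake are the primary and secondary responder rates in arms of about 12. The denominator wording adds an ambiguity. A subject whose only in-window value sits under TD does have an on-treatment measurement in the ordinary sense, so two programmers could count that subject differently.

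**Working it through.** **1. The plan's own interval.** SAP 2.3 gives 0.661 to 0.996 for 11 of 12 (exact, 90%). The Clopper-Pearson limits for x of n put 0.05 in each tail. For 11 of 12:

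- Lower limit L: P(X ≥ 11) = 12·L^11·(1 − L) + L^12 = 0.05, so L = 0.661.
- Upper limit U: P(X ≤ 11) = 1 − U^12 = 0.05, so U = 0.95^(1/12) = 0.996.

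The stated figure is reproduced.

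**2. Are visits kept on schedule affected?** Protocol Table 9 allows ± 2 days at Days 31, 61 and 91. I assume these windows are anchored to Day 1 and read the SAP filter as 25 to 35 days.

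| Trough | Shortest interval since dose | Longest interval since dose |
|---|---|---|
| Day 31 (dose on Day 1) | 29 − 1 = 28 | 33 − 1 = 32 |
| Day 61 (dose on Days 29 to 33) | 59 − 33 = 26 | 63 − 29 = 34 |
| Day 91 (dose on Days 59 to 63) | 89 − 63 = 26 | 93 − 59 = 34 |

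All lie within 25 to 35 days. No compliant trough is lost.

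**3. What the rules do with each kind of sample.**

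| Sample | Days since last dose | Responder rate under SAP 6.1 and Table 1 |
|---|---|---|
| Labelled Day 31, 61 or 91 | 25 to 35 | Counted |
| Labelled Day 31, 61 or 91 | More than 35 | Removed by the filter |
| Labelled unscheduled | 25 to 35 | Excluded, by explicit wording |
| Labelled TD | 25 to 35 | No stated route in (inferred) |

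Two limits apply to the last two rows. A redraw at Day 31 or 61 is a trough only if it precedes the next dose. The primary endpoint is the trough after the third dose, so a TD sample bears on Day 91 only in a subject who received that dose. A subject who stops after dose 1 or 2 can contribute only to Day 31 or Day 61.

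**4. Size of a loss.** A lost value leaves both numerator and denominator. Start from a full-data result of 11/12 = 0.917 (0.661 to 0.996):

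| Values lost | Rate | Exact 90% CI |
|---|---|---|
| One responder | 10/11 = 0.909 | 0.636 to 0.995 |
| The one non-responder | 11/11 = 1.000 | 0.762 to 1 |
| Two responders | 9/10 = 0.900 | 0.606 to 0.995 |
| One responder and the non-responder | 10/10 = 1.000 | 0.741 to 1 |

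For 11/11 the lower limit is 0.05^(1/11) = 0.762.

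**5. Late samples elsewhere.** SAP 7.9 has no day filter, so a late sample is summarised under its planned visit. For illustration, take the half-life of 20 to 28 days from Protocol 1.1 and assume simple exponential decline. A sample 14 days late then holds 2^(−14/20) = 62% to 2^(−14/28) = 71% of the on-time concentration. This concerns drug concentration only. The one lateness criterion in the SAP, "Out of window visit greater than 30 days" (section 5.4.1), belongs to the per-protocol set, whereas SAP 7.7 and 7.9 use the PK/PD set.

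**The case against.** The strongest reply is that the SAP already has a window where it matters. The ± 5 day filter governs the primary and secondary rates, PK parameters use actual times, and on-schedule troughs all pass. Analysis by nominal visit is a coherent choice for a descriptive phase 2a study with no significance tests. The examples also depend on labelling: a redraw on Day 93 is still inside the Visit 8 window and might be entered as Visit 8, and TD is a named visit, so the sentence on unscheduled visits does not cover it.

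Much of this stands. A reader might infer from "No visit windows will be applied for summary and analysis" that every analysis runs on labels alone and that late troughs are counted under their planned day. The documents do not support that: the filter removes a late trough from the responder rates, and those rates are proportions rather than means. A reader might also infer that the primary rate loses all early stoppers, but a subject who stops before dose 3 has no Day 91 trough to lose. Nor does Protocol 5.6 grant unlimited delay in sampling. It concerns doses, with resumption agreed case by case, and the Table 9 visit windows remain.

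The reply does not supply the missing rule. An unscheduled in-window value is excluded in plain words, and whether a TD value counts is left to the programmer.

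**Conclusion.** The gap is real but narrow. The SAP has a time-based filter and no time-based assignment. An in-window trough recorded as unscheduled is excluded from the Day 31, 61 and 91 responder rates. An in-window TD sample has no written way in, which I infer from the table layout and the absence of any mapping.

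One lost value out of 12 shifts the rate from 0.917 to 0.909 or 1.000. The lower limit moves to 0.636 or 0.762, so the error can go in either direction, and losing the non-responder flatters the dose. These figures assume 12 active subjects and 11 responders. The documents give no frequency for such samples, so the actual effect may be nil. With observed data only and no sensitivity analysis, however, nothing in the plan would reveal it.

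Late samples are a separate and lesser matter, confined to the descriptive by-visit summaries of SAP 7.9 and the mean plots.

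**What to change.** In SAP 6.1, define the trough after doses 1, 2 and 3 as the FXI value drawn 25 to 35 actual days after that dose and before any next dose. Apply this whatever the visit label, TD and unscheduled included. If several values qualify, take the one nearest 30 days. State that this rule overrides the nominal-visit and no-window sentences for the FXI responder endpoints, and that the SAP 7.7.1 denominator counts subjects with a value so assigned. The derivation should also say which dose counts as the first for a subject restarted under Protocol 5.6.

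The cost is SAP wording and one date-based derivation. The drawback is that a few values in the responder tables will come from non-standard visits, which a footnote can identify.

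I would not add exclusion windows for the other PK/PD visits. Any width would be a matter of preference and would remove subjects from descriptive summaries. At most, flag off-schedule samples in the listings.

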6.2 Handling of Dropouts, Missing Data, and Outliers

6.2.1 Study Discontinuation

Subjects who prematurely discontinue the study will undergo a study treatment discontinuation (TD) visit. Assessments performed at the TD visit are defined in appendix 4 of the protocol.

6.2.2 Missing Data

The occurrence of missing data related to the primary endpoint is considered a protocol deviation. Endpoint analyses will use observed data only – no imputation methods are planned.

Imputations of missing and partial dates are given below and to be used only for the following: assessment of treatment emergence status of an AE; determination of study day/time of onset and duration of an AE; definitions of prior and concomitant medications.

Missing or Partial Start Dates

- Missing time – the minimum possible onset time will be calculated and presented in '≥DD:HH:MM' format
- Missing day – impute the 1st of the month unless month is same as month of first dose of study drug then impute first dose date.
- Missing day and month – impute 1st January unless year is the same as first dose date then impute first dose date.
- Completely missing – impute first dose date unless the end date suggests it could have started prior to this in which case impute the 1st of January of the same year as the end date.

Missing or Partial End Dates

- Missing time – the maximum possible duration will be calculated and presented in '≤DD:HH:MM' format
- Missing day – impute the last day of the month unless month is same as month of first dose of study drug then impute last dose date.
- Missing day and month – impute 31st December unless year is the same as first dose date then impute last dose date.

CONFIDENTIAL

Page 14 of 28

Statistical Analysis Plan

Sponsor Name: Anthos
Sponsor Protocol ID: ANT-004

Covance Study ID: 000000189471

- Completely Missing – need to look at whether the AE/medication is still ongoing before imputing a date and when it started in relation to study drug. If the ongoing flag is missing, then assume that AE is still present / medication is still being taken (i.e., do not impute a date). If the AE/medication has stopped and start date is prior to first dose date then impute the 1st dose date, if it started on or after first dose date then impute a date that is after the last dose date.

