7.5.2 Previous and Concomitant Medications

Medications received prior to or concomitantly with study drug will be coded by Covance using the WHO Drug Version March 2019 Global Dictionary Version B3 Anatomical Therapeutic Chemical (ATC) Classification codes.

Prior medications and concomitant medications will be listed and summarized separately for per protocol set and FAS. The number and percentage of subjects using each medication will be displayed together with the number and percentage of subjects using at least one medication within each therapeutic class (ATC-Level 2), chemical subgroup (ATC-Level 4), and generic term.

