7.8.2 Adverse Events (AE)

All AEs recorded on the eCRF will be coded using the MedDRA dictionary version 22.0. Treatment-emergent Adverse Events (TEAEs) will be of primary interest and are defined as:

- AEs with a start date on or after the date of first dose of study drug and up to the EoS visit
- AEs with start date prior to the date of first dose of study drug whose severity worsens on or after the date of first dose of study drug

TEAEs will be summarized by system organ class (SOC) and preferred term (PT) by treatment group and overall. Subject counts and percentages and event counts will be presented for the following TEAE summaries:

- All TEAEs
- Serious TEAEs
- All TEAEs by severity
- All TEAEs by relationship to study drug
- TEAEs potentially related to study drug
- TEAEs potentially related to study drug by severity
- TEAEs leading to discontinuation of study drug
- TEAEs leading to withdrawal from study

A subject will only be counted once per SOC and once per PT. If a subject reports more than one AE with the same PT, the AE with the maximum severity will be presented. AE severity grades are mild, moderate, or severe. An AEs relationship to study drug is assessed as related, possibly related, or not related.

If the start date/time of an AE is incomplete or missing, the AE will be assumed to be a TEAE, unless the incomplete start date/time or the end date/time indicates an AE started prior to the start of the infusion. AEs with missing causality are assumed

Statistical Analysis Plan

Sponsor Name: Anthos

Sponsor Protocol ID: ANT-004

Covance Study ID: 000000189471

to be related. If the severity of an AE is missing, the AE will be counted under the maximum severity possible.

Listings will be presented by subject for TEAEs, AESIs, serious AEs (SAEs), AEs leading to discontinuation of study drug, and AEs resulting in death.

No statistical comparisons of AEs between treatment groups will be performed.

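### Two partial start-date rules in SAP 6.2.2 ignore the recorded end date and can place a start after its own end

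*SAP*

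**What the plan says.** SAP 6.2.2 imputes incomplete dates for three purposes: whether an AE is treatment-emergent, the onset day and duration of an AE, and the "definitions of prior and concomitant medications". Its start-date rules are:

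- *Day missing:* "impute the 1st of the month unless month is same as month of first dose of study drug then impute first dose date".
- *Day and month missing:* "impute 1st January unless year is the same as first dose date then impute first dose date".
- *Start date completely missing, with no part known:* "impute first dose date unless the end date suggests it could have started prior to this in which case impute the 1st of January" (in the year that the item ended).

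The third rule consults the end date. The first two do not.

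The imputed dates reach reported output. SAP 7.5.2 states: "Prior medications and concomitant medications will be listed and summarized separately for per protocol set and FAS". SAP 7.1 (Table 1) calls for listings of derived data as well as collected data. For AEs, SAP 7.8.2 adds a separate rule: "If the start date/time of an AE is incomplete or missing, the AE will be assumed to be a TEAE", with an exception, "unless the incomplete start date/time or the end date/time indicates an AE started prior to the start of the infusion". The study drug is given subcutaneously, so I read the infusion there as the first dose.

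**The concern.** A record can carry a partial start and a full end date that precedes dosing. Such records are plausible here. Protocol 7.6.1 collects AEs from informed consent, and Protocol Table 9 runs screening from Day -28 to Day -3, so an event can begin and resolve before the first injection but within the same month or year. A drug stopped earlier in that year is just as ordinary.

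For such a record, the partial-date rules override what is known (the item was over before dosing) with an imputed start that cannot be true. Three results follow:

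- The start is later than the end.
- Any duration derived from the two dates is negative.
- A medication stopped before the first injection carries a start on Day 1, and any classification that uses the start date will call it concomitant.

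This is a stated rule that yields an impossible value, rather than a detail left for programming.

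**Working it through.** No figure in the plan bears on this point, so there is none to reproduce. The check applies the written rules to dated examples. The documents give no subject dates, so the dates below are assumptions. I read a matching month as the same month of the same year, which is the reading more favourable to the plan.

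**Step 1. Apply the rules as written.**

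| Case | Recorded start | Recorded end | First dose | Rule used | Imputed start | Imputed start minus end |
|---|---|---|---|---|---|---|
| 1 | March, day missing | 12 March | 20 March | Day missing | 20 March | 20 − 12 = 8 days |
| 2 | Sep 2020, day missing | 5 Sep 2020 | 15 Sep 2020 | Day missing | 15 Sep 2020 | 15 − 5 = 10 days |
| 3 | 2020 only | 30 Apr 2020 | 15 Sep 2020 | Day and month missing | 15 Sep 2020 | 31 + 30 + 31 + 31 + 15 = 138 days |
| 4 | Completely missing | 30 Apr 2020 | 15 Sep 2020 | Completely missing | 1 Jan 2020 | start precedes end |
| 5 | 2015 only | ongoing | 15 Sep 2020 | Day and month missing | 1 Jan 2015 | no end date |

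Cases 1 to 3 are impossible. Case 4 is coherent, because that rule looks at the end date. With its exception triggered by an end before first dose, that rule gave no start after end over 1,900 successive end dates. Case 5 shows that a partial start outside the month or year of first dose is not moved to Day 1.

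Under the study-day convention in SAP 6.1, Case 1 would be listed as starting on Day 1 and ending on Day −8.

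**Step 2. How much of the date space is exposed.** Take a period of N days (a month or a year) with first dose on its day d, and suppose the true start and end both lie in that period. There are N(N + 1)/2 pairs with start no later than end. In d(d − 1)/2 of them the end precedes first dose, and these are the pairs that fail. The failing share is d(d − 1) / [N(N + 1)].

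- Month rule, N = 30, d = 15: 105/465 = 22.6%.
- Year rule, N = 366 (2020), N(N + 1)/2 = 67,161:
  - first dose 1 March (d = 61): 1,830/67,161 = 2.7%
  - 15 June (d = 167): 13,861/67,161 = 20.6%
  - 15 September (d = 259): 33,411/67,161 = 49.7%
  - 1 December (d = 336): 56,280/67,161 = 83.8%

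These shares treat every pair as equally likely and condition on a matching partial start with an end in the same period. They show that the failure is no corner case of the rule. They do not estimate how many records in this trial are affected.

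**Step 3. Is the gap closed elsewhere?** SAP 7.8.2 would keep an AE such as Case 1 out of the treatment-emergent set, because its end date shows an earlier start. It does not alter the imputed onset day or the duration, and it does not cover medications. SAP 7.5.2 has no end-date check either.

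**Step 4. Effect of the repair.** If first dose is imputed only when the end is missing, ongoing, or on or after first dose, Case 1 starts on 1 March (11 days before its end), Case 2 on 1 Sep 2020 (4 days before) and Case 3 on 1 Jan 2020 (120 days before). Cases 4 and 5 are unchanged. An end date consistent with its own partial start cannot precede the 1st of that month or 1 January of that year, so the repair leaves no start after end.

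**The case against.** The strongest reply is that this is small. Moving AE starts to first dose is the conservative choice for treatment emergence, and SAP 7.8.2 removes events that plainly ended earlier. The AE summaries specified there include no table of onset day or duration, so a negative duration would appear at most in a listing. Protocol 6.1 asks sites to record medication start and stop dates, so incomplete dates may be few. Because SAP 7.5.2 does not define prior and concomitant by date, a program that classed by end date would still call the Case 1 drug prior. All of this stands as a limit on size. None of it makes a start after the end acceptable.

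A reader might also infer three stronger things that the documents do not support.

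- *That prior use of the permitted low-dose aspirin is understated.* A drug of unknown start that is still being taken does get a Day 1 start. Whether it then leaves the prior table depends on a start-based definition of prior that SAP 7.5.2 does not give. The drug still counts as concomitant, which is the exposure relevant to bleeding on treatment, and the medication tables show use by class and generic term without start day.
- *That the 1 January exception can itself land after first dose.* It can only if an end date after first dose is taken to suggest an earlier start. The natural trigger is an end before first dose, and 1 January of that year is then also before first dose.
- *That all partial starts are pushed to Day 1.* Case 5 shows that they are not.

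**Conclusion.** The point holds for the two partial-date start rules. Read literally, they impute the first dose date on a matching month or year without checking the recorded end. They therefore give a start after the end for any AE or medication that finished before dosing in that month or year.

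The negative duration follows from the text alone. The misclassification of a stopped medication as concomitant is possible but not certain, because it depends on how the program defines the classes.

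The consequence is minor. It is limited to descriptive medication tables and AE and medication listings. The number of affected records cannot be known from the documents. SAP 6.2.2 restricts endpoint analyses to observed data, so the primary endpoint is unaffected.

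**What to change.** In SAP 6.2.2, add one condition to each of the two partial-date start bullets: impute the first dose date only if the recorded end date is missing, the item is ongoing, or the end falls on or after first dose. Otherwise impute the 1st of the recorded month (day missing) or 1 January of the recorded year (day and month missing). State the principle alongside: no imputed start may be later than the recorded end.

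The completely-missing rule needs no change for this purpose. The cost is one line of text per bullet and the matching programming condition, with no effect on the primary analysis.

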The study is comprised of 3 periods: screening period, treatment period, and follow-up period. The screening period may last up to 4 weeks. The treatment period is 91 days and consists of 3 monthly subcutaneous doses of MAA868 (or matching placebo). Study drug is administered at the study site on day 1 (visit 2), day 31 (visit 4), and day 61 (visit 6). During the treatment period, subjects will return to the study site on day 11, day 31, day 41, day 61, day 71, and day 91 for safety assessments. The follow-up period is 79 days and continues to day 170, allowing a 110-day washout period from the last study drug administration. During the follow-up period, subjects will return to the study site on day 101, day 121, and day 170 (EoS) for additional safety evaluations.

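### SAP 6.2.2: the two last-dose-date exceptions for partial end dates give dates that contradict the recorded month or year, or that fall before the event began

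*SAP*

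**What the plan says.** SAP 6.2.2 (Missing Data) limits date imputation to a few uses: AE treatment emergence, and "determination of study day/time of onset and duration of an AE; definitions of prior and concomitant medications". For partial end dates it gives two rules, each with an exception:

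- Day missing: "impute the last day of the month unless month is same as month of first dose of study drug then impute last dose date".
- Day and month missing: "impute 31st December unless year is the same as first dose date then impute last dose date".

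The matching start-date rule for a missing day is different in kind: "impute the 1st of the month unless month is same as month of first dose of study drug then impute first dose date". No sentence in the section requires an imputed end to stay within the recorded month or year, or to fall on or after the start.

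SAP 2.2 places the doses on Days 1, 31 and 61 and adds that "The follow-up period is 79 days and continues to day 170, allowing a 110-day washout period from the last study drug administration". SAP 7.8.2 counts as treatment-emergent "AEs with a start date on or after the date of first dose of study drug and up to the EoS visit", so events that begin well after the last dose are in scope. Protocol 5.6 foresees subjects with a single dose: "Subjects who received only 1 dose of study drug before interruption may either resume study drug with the second dose".

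**The concern.** The start-date exception moves a date to the first dose, which by construction lies in the recorded month. The end-date exceptions move it to the last dose, which need not lie in the recorded month or year and need not follow the event's start. An imputation rule may fill in what is unknown. It should not overwrite what is known, and here the month, the year or the order of start and end can be overwritten.

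At stake is the derived AE duration, a use that SAP 6.2.2 names. Each cohort has 12 active subjects, so events will be read one at a time in listings. A negative duration, or an end date two months after the recorded month, would be plainly visible there.

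**Working it through.** The plan states no figure to reproduce, so the check applies the rules by calendar arithmetic.

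**Inputs.** Last planned dose 60 days after the first (SAP 2.2: Day 61 − Day 1). End of study Day 170 (SAP 2.2). Window for the Day 61 visit ±2 days (Protocol Table 9). Assumption: 'same month' means same month and year, except where the literal reading is tested.

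**1. Day missing, three doses.** Let d be the day of the month of first dose and M the length of that month. The imputed end lies 60 − (M − d) days past the last day of the recorded month.

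- Smallest: d = 1, M = 31 gives 60 − 30 = 30 days.
- Largest: d = M gives 60 − 0 = 60 days.
- Over every first-dose date, Day 61 falls in the first-dose month for 0 of 366 dates in 2020 and 0 of 365 in 2021. The mean overshoot is about 45 days. Taking the last dose 2 days early or late still gives 0 and shifts the range to 28–58 or 32–62 days.

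The contradiction with the recorded month is therefore certain. The end cannot precede the start here, because the imputed date is too late, not too early.

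**2. Day missing, one dose.** Last dose equals first dose. An event that starts later in that month and ends in it receives an end before its start. This is possible for 354 of 366 first-dose dates in 2020, that is, all but the last day of each of the 12 months.

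**3. Day missing, literal reading.** The rule compares months and does not mention the year. A medication stopped in the same calendar month of an earlier year would be moved to the last dose date and become concomitant.

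**4. Day and month missing.** Any event that starts after the last dose in the first-dose year gets an end before its start. For a Day 100 start, 61 − 100 = −39 days. In 2020 this can occur for first doses up to 31 October (305 of 366 dates), and it covers about 69% of Days 62–170 taken over all first-dose dates. From 2 November (60 of 366 dates) Day 61 falls in the next year, so the imputed end contradicts the recorded year instead.

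**Worked cases.** Assumed first dose 15 July 2020, so Day 61 is 13 September and Day 170 is 31 December. Durations count both end days.

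| Case | SAP rule | Last date compatible with the record |
|---|---|---|
| AE from 20 July, end July 2020, three doses | 13 September, 56 days | 31 July, 12 days |
| Same AE, one dose | 15 July, 5 days before start | 31 July, 12 days |
| AE from 20 October, end 2020 | 13 September, 37 days before start | 31 December, 73 days |
| Medication stopped July 2018 (literal reading) | 13 September 2020, concomitant | 31 July 2018, prior |

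**The case against.** The strongest reply is that almost nothing reported depends on these dates, and most of it stands.

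- **Medication status.** A reader might infer that a drug stopped in the first-dose month, before dosing, is wrongly turned into a concomitant one. The documents do not support that as a consequence of the exception. SAP 7.5.2 gives no cut-off. On the usual assumption that a medication ending on or after first dose is concomitant, the last dose date and the last day of the first-dose month both give that label. The same holds for the last dose date and 31 December. A difference could arise only at a same-day boundary for a one-dose subject, or under the literal earlier-year reading. SAP 7.5.2 tabulates use, not overlap with individual doses.
- **Treatment emergence.** A reader might infer that TEAE counts shift. SAP 7.8.2 sets the status by start date or worsening severity. End dates enter only as evidence of onset before dosing, and in the first-dose month or year neither rule yields an end before first dose.
- **AE tables.** None of the eight TEAE summaries in SAP 7.8.2 uses duration. Injection-site reaction duration (SAP 7.8.7) is recorded in categories at inspection. Bleeding and thromboembolic events are counts.
- **Rarity.** Protocol 7.6.1 asks for start and end dates, or an unresolved outcome, and for follow-up until an event resolves or is judged permanent. Year-only end dates should be uncommon, and the documents give no frequency.

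What does not stand is a defence of the rule as a conservative convention. It overstates duration in one branch and can make it negative in the other, whereas for missing times the same section takes the longest possible duration. No other text corrects it.

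**Conclusion.** The two exceptions are wrong as written, and the point is minor. They fail separately. The missing-day exception contradicts the recorded month for every three-dose subject it touches, by 30 to 60 days on the planned schedule, and can put the end before the start for a one-dose subject. The year-only exception can put the end before the start for events that begin after the last dose, or leave the recorded year for first doses from 2 November. It would be wrong to merge these into one claim: the missing-day rule cannot produce a negative duration in a three-dose subject, and the year-only rule has no recorded month to contradict.

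The effect is on derived AE durations and end dates in listings. The primary endpoint is untouched, since SAP 6.2.2 analyses endpoints on observed data without imputation. The counts assume dosing on the planned days. A last dose delayed by an interruption under Protocol 5.6 would lengthen the error in the missing-day branch. The number of subjects affected cannot be estimated from the documents.

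**What to change.** In SAP 6.2.2, delete the last-dose-date exception from both partial end-date rules. With the day missing, impute the last day of the recorded month. With day and month missing, impute 31 December of the recorded year. In both cases cap the result at the end-of-study or last-contact date, or the date of death, and do not let it precede the start date. Removing the month comparison also disposes of the earlier-year ambiguity.

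The cost is two lines of SAP text and a small programming change. No data collection, planned table or sample size is affected.
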